9.11. Strengths and Limitations of the Research Methods

In the absence of a suitable existing database, this retrospective medical record review will allow the collection of real-world data in adult patients who received isavuconazole for the treatment of invasive aspergillosis or mucormycosis in the hospital setting. Unlike a prospective study, retrospective cohort designs are not sensitive to the Hawthorne effect (ie, alteration of behavior and/or prescribing practices as a result of being observed).

Limitations of this retrospective study design are acknowledged and will be documented within the study report:

- Data quality will be dependent on completeness and accuracy of the data abstraction and the data documentation in the medical records. Differences in how each site operates, the connections to other health care facilities within the medical record, and the extent to which specific details are documented will affect data availability across medical records. For example, it is expected that the timing of follow-up visits may vary across sites. Additionally, some data are less likely to be comprehensively documented, including reasons for treatment modification/discontinuation/switching, TDM, mycological/radiological response status at end of treatment, AEs, and reason for HCP visits/referrals. Moreover, visits that occur at a different site may not be documented within the medical record to which the site has access; thus, the data may not provide an accurate representation of the true health care burden. A rigorous data review and cleaning process will be undertaken to ensure that the data which is collected is of the highest quality for analysis.
- The study sites will be chosen based on a convenience sampling approach. That is, sites that indicated interest in study participation and that retain pertinent data within patient medical records that meet the study eligibility criteria were identified during the feasibility assessment. Therefore, by study design, the sites are unlikely to be fully representative of all sites in which cases of invasive aspergillosis or mucormycosis are managed with isavuconazole therapy. Thus, the data are unlikely to be representative of the overall usual care patterns for invasive aspergillosis or mucormycosis in Europe, and the study results should not be considered to be generalizable.

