## 6 STATISTICAL METHODS AND ANALYSIS

### 6.1 STATISTICAL CONVENTIONS

Categorical variables will be reported as counts and frequencies of nonmissing observations. Continuous variables will be reported using the number of nonmissing observations, mean, standard deviation, median, first quartile, third quartile, minimum value, and maximum value. Time-to-event outcomes will be assessed using the Kaplan-Meier (KM) method and will be reported as descriptive statistics with 95% CIs. Results will be presented for the overall group (both disease types) and separately for invasive aspergillosis and mucormycosis. Additionally, subgroup analyses may be performed. If so, log-rank tests will be reported, and Cox regression will be employed with presentation of hazard ratios (HRs) and 95% CIs.

Unless otherwise specified, the time between two dates of interest (including time-to-event analyses) will be computed as the difference between the two calendar dates (e.g., date 2 – date 1) and expressed in days.

No imputation for missing values will be performed. Criteria for censoring in KM analyses will be described for each time-to-event outcome analyzed.

Example tables and figure descriptions for analyses described in this section (analysis tables and analysis figures) are provided in Appendix 1.

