### 6.3 ANALYSIS OF CLINICAL OUTCOMES

Each clinical outcome will be analyzed using counts and frequencies at weeks 6, 12, and 24, along with other descriptive information about the clinical outcome itself.

Additionally, time-to-event analyses anchored on the index date of isavuconazole initiation will be performed using the KM method. For each clinical outcome, the time-to-event analyses will result in a KM plot with summary statistics, including survival-time quartiles and KM estimates at weeks 6, 12, and 24 with accompanying 95% CIs. All analyses will be performed for invasive aspergillosis patients, mucormycosis patients, and for the total study population. If subgroup analyses are pursued, Cox regression will be employed to derive HRs and accompanying 95% CIs.

For the death outcome, patients will be categorized as dead, alive, or unknown at each timepoint of interest, and primary cause of death will be tabulated (Appendix 1, Analysis Table 5.1). For KM analyses, a documented death will comprise the event, and patients will be censored at the date when they are last known to be alive (Appendix 1, Analysis Figure 1; Appendix 1, Analysis Table 5.2).

For the clinical response outcome, patients will be categorized as having clinical success, having clinical failure, or unknown response at each timepoint of interest will be tabulated (Appendix 1, Analysis Table 6.1). In addition, rates of reactivation of the same infection and rates of new infection will be documented overall and specific to whether these events occurred during isavuconazole treatment. For KM analyses, clinical response will comprise the event, and patients will be censored at the earliest timepoint of any of the following: loss to follow-up, end of study, or death (Appendix 1, Analysis Figure 2; Appendix 1, Analysis Table 6.2).

For radiological response, patients will be categorized as having a success, not having a response, unknown response, or not applicable (for the first assessment) at the relevant timepoints of interest (Appendix 1, Analysis Table 7.1). Additionally, radiological examination type and bodily location of the examination will be tabulated. For KM analyses, radiological response will comprise the event, and patients will be censored at the earliest timepoint of any of the following: loss to follow-up, end of study, or death (Appendix 1, Analysis Figure 3; Appendix 1, Analysis Table 7.2).

PFIZER CONFIDENTIAL

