CT24-WI-GL03-RF03 1.0 *Non-Interventional Statistical Analysis Plan For Secondary Data Collection*  
Study 16-Sep-2020  
Page 15 of 19

For the mycological response outcome, patients will be categorized having the infection eradicated, presumed eradicated, not eradicated (failure), unknown response, or not applicable (for the initial assessment) at relevant timepoints of interest. Additionally, mycological examination type and biomarker categories will be tabulated at post-baseline visits (Appendix 1, Analysis Table 8.1). For KM analyses, mycological response (eradication or presumed eradication) will comprise the event, and patients will be censored at the earliest timepoint of any of the following: loss to follow-up, end of study, or death (Appendix 1, Analysis Figure 4; Appendix 1, Analysis Table 8.2)

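### The Kaplan-Meier response curves in SAP 6.3 count follow-up time without any response assessment as event-free time, and the same rule also censors at death

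*SAP*

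**What the plan says.** SAP 6.3 plans a Kaplan-Meier (KM) curve for each response type, with estimates at weeks 6, 12 and 24 and time-to-response quartiles.

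- **Clinical:** "clinical response will comprise the event, and patients will be censored at the earliest timepoint of any of the following: loss to follow-up"; the other two endpoints are death and the end of the study.
- **Radiological:** "radiological response will comprise the event, and patients will be censored at the earliest timepoint of any of the following: loss to follow-up", with the same two further endpoints.
- **Mycological:** "mycological response (eradication or presumed eradication) will comprise the event, and patients will be censored at the earliest timepoint" of the same three.

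For death the rule differs: "patients will be censored at the date when they are last known to be alive".

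SAP 6.1 adds: "No imputation for missing values will be performed. Criteria for censoring in KM analyses will be described for each time-to-event outcome analyzed". SAP 3 runs every analysis on the whole analysis population, which includes suspected as well as confirmed diagnoses. SAP Table 1 ties mycological success to the organism originally cultured.

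The count tables in SAP 6.3 keep an unknown category. For clinical response, "patients will be categorized as having clinical success, having clinical failure, or unknown response at each timepoint of interest". No section says how an unknown response enters the KM curve. The SAP does not define loss to follow-up or end of study; SAP 4.2 uses the former for the patient's overall follow-up.

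Protocol 9.11 lists "mycological/radiological response status at end of treatment" among the items less likely to be fully documented, and expects follow-up visit timing to vary by site. Protocol 9.9.1 leaves censoring methods to the SAP.

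**The concern.** A response can be recorded only at an assessment of that type. For death, the SAP stops the clock when status was last known. For response, the clock runs on while the patient is merely in contact. A patient whose last scan is at week 3 and who is still attending at week 24 adds 21 weeks of apparent non-response. A patient with no scan after index adds non-response from day 0. A suspected case with no cultured organism can hardly have a mycological event at all, yet stays in that risk set.

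Overall response is part of a primary objective, and protocol 9.9.2.1 puts KM time to response in the primary analysis plan. The distortion grows as documentation gets poorer, so it can differ by response type and site. It could also affect the optional subgroup log-rank and Cox results if documentation differs between groups.

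**Working it through.** The documents give no response rate, assessment rate or KM figure for this study, so there is no planned figure to reproduce. The inputs below are assumptions, except the day-42 mortality figures, which come from protocol 7.2 (19%, SECURE) and 7.3 (33% weighted, VITAL).

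**1. Share q never assessed, no deaths.** Let F(t) be the true cumulative response, and let missing assessment be unrelated to response. The observed event-free share is q + (1-q)(1-F(t)), so the planned estimate is

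1 - KM(t) = (1-q) × F(t).

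With F = 60% at week 12:

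| q | planned estimate |
|---|---|
| 10% | 0.9 × 60 = 54% |
| 20% | 0.8 × 60 = 48% |
| 30% | 0.7 × 60 = 42% |
| 40% | 0.6 × 60 = 36% |

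A second pattern, with response seen only at fixed visits and true values 30/48/60% at weeks 6/12/24, gives the same factor. At q = 20% the planned curve reads 24/38/48%, and the median moves from week 24 to not reached.

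**2. Assessment stops early, no deaths.** Take exponential response with 60% by day 84: λ = -ln(0.4)/84 = 0.01091 per day, so F is 84% at day 168. Let 30% of patients have their last scan uniformly on days 14 to 56. Their mean response by the last scan is

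1 - (e^(-14λ) - e^(-56λ))/(42λ) = 1 - (0.8584 - 0.5429)/0.4581 = 0.311.

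- Week 12: 0.7 × 0.60 + 0.3 × 0.311 = 51%, against 60%.
- Week 24: 0.7 × 0.84 + 0.3 × 0.311 = 68%, against 84%.

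**3. Adding deaths.** Let 19% die by day 42 at a constant hazard unrelated to response: μ = -ln(0.81)/42 = 0.00502 per day. The proportion who respond while alive is

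λ/(λ+μ) × (1 - e^(-(λ+μ)t)).

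- Week 12: 0.685 × (1 - 0.2624) = 0.505, about 51%.
- Week 24: 0.685 × (1 - 0.0689) = 0.638, about 64%.

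With death censored, the planned estimate is still (1-q) × F(t):

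| | week 12 | week 24 |
|---|---|---|
| Respond while alive | 51% | 64% |
| Planned rule, q = 10% | 54% | 76% |
| Planned rule, q = 20% | 48% | 67% |
| Planned rule, q = 30% | 42% | 59% |
| Last-assessment censoring, death still censored | 60% | 84% |
| Last-assessment censoring, death as competing event | 51% | 64% |

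The planned rule changes from too high to too low at q = 1 - 0.505/0.60 = 16% (week 12) and q = 1 - 0.638/0.84 = 24% (week 24). With 33% dead by day 42, μ = 0.00954, the week-12 value is 0.534 × (1 - 0.180) = 44%, and the change of sign comes at q = 1 - 0.438/0.60 = 27%.

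**4. Irregular detection, no deaths.** Simulate the response times of step 2, seen only at one to three scans on random days 7 to 175. True response at weeks 6/12/24 is 37/60/84%. The planned rule gives 9/27/65%; last-assessment censoring gives 9/30/89%. At weeks 6 and 12 almost all the shortfall is detection delay, which censoring does not repair. At week 24 the revised censoring overshoots by 5 points.

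**The case against.** The strongest reply is that the curve describes time to first documented response. Counting unknown as no event is a recognised conservative convention, and protocol 9.9.2.1 does speak of response as documented in the record. Sites are selected for response documentation, the tables show unknowns separately, and protocol 9.9.1 has missing data counted and discussed. The study is descriptive. This stands in part: it supports keeping the current rule as a labelled analysis and lowers the severity. It does not excuse leaving the convention unstated, since unknown remains a permitted answer and protocol 9.11 expects gaps.

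Loss to follow-up could be read as the last assessment of that type. The SAP does not say so, and SAP 4.2 points the other way.

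Three stronger readings are tempting, and the documents do not support them.

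- **The planned estimates are biased low.** Step 3 shows that the sign depends on q and on mortality, because the same sentence censors at death.
- **The table and the curve for one outcome contradict each other.** Status at a timepoint and time to first documented response are different quantities.
- **All three curves are equally affected.** Protocol 9.11 names radiological and mycological status at end of treatment, not clinical response.

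New censoring alone is not a remedy either. With death still censored it gives 60% against 51% in step 3, further off than the planned rule at q = 10% or 20%. It also assumes that missing an assessment is unrelated to response; if deteriorating patients go unscanned, it overstates response.

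**Conclusion.** The point holds as a defect in the stated censoring rule. Patients without a further assessment of a response type, or without any, contribute event-free time until they leave follow-up or die. Alone, this multiplies the estimate by (1-q) when a share q is never assessed and missingness is unrelated to response: an assumed 60% becomes 54% at q = 10% and 42% at q = 30%. It weighs most on radiological and mycological response, and most clearly on mycology in patients with no cultured organism.

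Neither the net direction nor the real size can be given. Both depend on assessment rates that the documents do not report and on mortality in this cohort. The figures with deaths further assume constant hazards and death unrelated to response. In a descriptive study whose tables already show unknowns, this is a should-fix.

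**What to change.** In SAP 6.3, for each response type:

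1. Limit the risk set to evaluable patients (for mycology, those with an organism identified at baseline) and report under each curve how many were excluded as unknown.
2. Censor patients who are alive without response at their last evaluable assessment (success or failure) of that type.
3. Treat death before response as a competing event and report cumulative incidence. Do not make change 2 without this one.
4. State how long after the last evaluable assessment a death still counts as the competing event. Counting every later death while censoring survivors earlier would over-weight death. Apply the same interval from index, so that patients who die before any assessment are not dropped as unknown.
5. Define loss to follow-up and end of study.
6. Keep the current rule as a companion analysis, labelled as unknown counted as no documented response.

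The cost is a few lines of SAP text and one extra curve per outcome; protocol 9.4.3 already collects the assessment dates. The SAP should state the downsides: wider late confidence intervals, felt most in the small mucormycosis group; the assumption that missing assessment is unrelated to response; and detection delay from irregular visits, which remains.

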#### **6.4 ANALYSIS OF SAFETY OUTCOMES**

Descriptive statistics will be used to tabulate the occurrence of AEs at week 6 (Appendix 1, Analysis Table 9.1), week 12 (Appendix 1, Analysis Table 9.2), and week 24 (Appendix 1, Analysis Table 9.3). These tables will be repeated for SAEs (Appendix 1, Analysis Tables 10.1, 10.2, and 10.3, respectively). Additionally, these tables will summarize the occurrence of any AE, number of AEs, isavuconazole-related AEs, whether action was taken with isavuconazole, and the AE outcome.

KM plots for time to onset of the first AE will be generated (Appendix 1, Analysis Figure 5), and summary KM statistics will be tabulated (Appendix 1, Analysis Table 11). For KM analyses, onset of the first AE will comprise the event, and patients will be censored at the earliest timepoint of any of the following: loss to follow-up, end of study, or death.

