	
 • Dyspepsia; • Constipation; • Abdominal distension; • Other (specify). • Hepatobiliary AE: 
 • Elevated liver chemistry tests (alanine aminotransferase [ALT], aspartate aminotransferase [AST], alkaline phosphatase, bilirubin); • Hepatomegaly; • Hepatitis; • Other (specify). • Skin and subcutaneous tissue AE: 
 • Rash; • Pruritus; • Petechiae; • Alopecia; • Drug eruption; • Dermatitis; • Other (specify). • Musculoskeletal and connective tissue AE: 
 • Back pain; • Other (specify). • Renal and urinary AE: 
 • Renal failure; • Other (specify). • General disorders and administration site condition AE: 
 • Chest pain; • Fatigue; • Injection site reaction; • Edema peripheral; • Malaise; • Asthenia; • Other (specify). • Other AE (specify). 	
AE onset date (DD MMM YYYY)		
AE resolution:		

 • Yes; • No; 		

Category	Variable	Timepoint
	
 • Unknown. 
AE resolution date (DD MMM YYYY)
	
	
AE seriousness:
 
 • Was life-threatening; • Required inpatient hospitalization or prolongation of existing hospitalization; • Resulted in persistent or significant incapacity or disability; • Was a congenital anomaly/birth defect; • Was a medically important event; • Resulted in death; • None of the above; • Unknown. 	
	
AE severity:
 
 • Mild; • Moderate; • Severe; • Unknown. 	
	
Documented relationship to isavuconazole:
 
 • Yes; • No; • Unknown. 
Action taken with isavuconazole:
 
 • Treatment discontinuation; • Dose reduced; • Dose increased; • Dose delayed; • Dose not changed; • Not applicable; • Unknown. 	
	
Outcome of event:
 
 • Resolved; • Resolving; • Resolved with sequelae; • Not resolved; • Fatal; • Unknown. 	

AE = adverse event; ICD-9 = International Classification of Diseases, 9th Revision; ICD-10 = International Classification of Diseases, 10th Revision.

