9.9.2. Planned Analysis

9.9.2.1. Analysis Plan for Primary Objectives

Mortality/survival rates will be summarized and reported. Clinical, radiological, and mycological response documented in the medical record will be summarized using proportions and counts for each category. Details of radiological and mycological assessments will be reported in a descriptive manner, including the type of assessment and the assessment findings. Definitions of response will be provided in the SAP. Time to response and all-cause mortality will be analyzed using the KM method and quartiles and 95% CIs will be reported.

Descriptive statistics will be used to describe all AEs and SAEs reported during the medical record review. The safety data described will include event type, relationship to isavuconazole treatment (where known), event severity, event seriousness, action taken with isavuconazole treatment and outcome of the event. Definitions of AEs and SAEs will be described in the SAP. Time from index treatment to first AE onset will be summarized.

Key timepoints of interest for assessment of treatment effectiveness, safety and survival outcomes will be at 6 weeks, 12 weeks, and 24 weeks after initiation of index treatment. In the cases that usual care visits do not directly coincide with these timepoints, the time windows for assessment of outcomes will be defined in the SAP.

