### 2.2 STUDY OBJECTIVES

#### *Primary Objectives*

- *To document real-world clinical outcomes (all-cause mortality, overall response) of isavuconazole in patients with invasive aspergillosis or mucormycosis receiving treatment in routine clinical practice in Europe*
- *To assess real-world safety (isavuconazole-related AEs and SAEs) of isavuconazole in patients with invasive aspergillosis or mucormycosis receiving treatment in routine clinical practice in Europe*

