Mycological response	
Mycological success will be defined as eradication or presumed eradication of the original causative organism cultured.
 
Mycological failure will be defined as persistence or presumed persistence.
 
When medical record documentation is not clear to the abstractor as to which category should be specified, the investigator should review all available medical record documentation to determine classifications. If the investigator determines there is not enough medical record documentation to make the classification, he or she will indicate that the response is 'unknown.' Since mycological response classification is important to the study, participating sites will be selected for participation in the study based on their reporting whether they have enough medical record documentation to classify the response.
	Post-index period

PFIZER CONFIDENTIAL

CT24-WI-GL03-RF03 1.0 *Non-Interventional Statistical Analysis Plan For Secondary Data Collection*  
 Study 16-Sep-2020  
 Page 12 of 19

Variable	Definition	Timepoint
Adverse events	Documentation of any adverse event in the medical record or as described by the ICD-9 or ICD-10 systems.	Post-index period
Serious adverse event	Documentation of any serious adverse event in the medical record or as described by the ICD-9 or ICD-10 systems.	Post-index period
Treatment patterns	Documentation of any of the following in the medical record: 
 
• Index treatment modification
 
• Index treatment discontinuation
 
• TDM
 
• Switching to a new antifungal therapy after index treatment discontinuation
 
• Use of subsequent antifungal therapy after end of index treatment
 
• Index treatment administered as part of antifungal combination therapy
 
• Other concomitant treatments not including combination antifungal therapy
 
• Index treatment administered in the outpatient setting following initiation in the inpatient setting
 
	Post-index period
Healthcare resource utilization	Documentation of any inpatient stay (including specialty wards, ICU, ER, general medicine ward, or other) or outpatient visit (not associated with a hospitalization) in the medical record.	Post-index period

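### The only time-to-event safety analysis uses the first AE of any cause, while the primary safety objective is isavuconazole-related AEs and SAEs

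*SAP*

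**What the plan says.** The primary safety objective in SAP 2.2 is "To assess real-world safety (isavuconazole-related AEs and SAEs) of isavuconazole in patients with invasive aspergillosis or mucormycosis"; Protocol section 8 sets the same objective.

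SAP Table 1 defines an adverse event by "Documentation of any adverse event in the medical record or as described by the ICD-9 or ICD-10 systems", without reference to cause. In SAP 6.4, "KM plots for time to onset of the first AE will be generated" (Analysis Figure 5, with summary statistics in Analysis Table 11), and "onset of the first AE will comprise the event". Patients without an event are censored when follow-up is lost, the study ends or they die; stopping isavuconazole does not end time at risk. SAP 4.2 lets the post-index period run to 6 months after discontinuation. Protocol 9.3.1.3 has the same rule and adds a cap at 31 December 2019.

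SAP 6.4 also plans AE tables at weeks 6, 12 and 24, repeated for SAEs: "these tables will summarize the occurrence of any AE, number of AEs, isavuconazole-related AEs, whether action was taken with isavuconazole, and the AE outcome". No time to first related AE or to first SAE is named.

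The SAP here follows the protocol, whose section 9.9.2.1 says "Time from index treatment to first AE onset will be summarized". Protocol 9.4.4 collects, for each AE, an onset date and the field "Documented relationship to isavuconazole" (Yes, No or Unknown).

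**The concern.** The event in the curve is not the event in the objective. This has three consequences.

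- A patient leaves the risk set at the first AE, whatever its cause. A related AE or SAE that comes later cannot appear in the analysis.
- Protocol 9.11 expects severe underlying disease. Neutropenia appears both among the baseline comorbidities (Protocol 9.4.1) and among the AE terms (9.4.4), as one example of how background illness can supply the first event.
- Time off drug counts, for up to 6 months.

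At stake is how early and how often drug-related harm appears, with its uncertainty. Under SAP 6.1, categorical results are counts and frequencies of non-missing observations, and 95% CIs are attached to time-to-event outcomes. On the SAP text, the any-cause endpoint gets an interval and a censoring rule, and the endpoint named in the objective gets neither.

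**Working it through.** **1. Text comparison.** The plan gives no figure to reproduce; the main check sets the passages side by side.

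| Element | Objective (SAP 2.2, Protocol 8) | Time-to-event analysis (SAP 6.4) | Tables at weeks 6, 12, 24 (SAP 6.4) |
|---|---|---|---|
| Cause | Isavuconazole-related | Any | Any, with related AEs summarized |
| Seriousness | AEs and SAEs | Any AE; none for SAEs | AE tables, repeated for SAEs |
| Later related event after an unrelated one | Relevant | Not visible | Can be counted |
| CI and censoring rule in the SAP text | Not applicable | Yes (SAP 6.1, 6.4) | None stated |

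**2. How far could the two curves differ?** This is an illustration, not an estimate.

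Inputs:
- Related-AE risk p_r = 42%, the SECURE figure in SAP 1.2 and Protocol 7.2. Assumed to apply over 24 weeks.
- Any-AE risk p_a. The documents give none; assumed range 60% to 95%.
- Constant hazards, related and unrelated events independent, deaths ignored.

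Formulas: h = −ln(1 − p)/24 per week; related share of first AEs = h_r/h_a; median = ln 2/h; week-6 risk = 1 − exp(−6h).

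Related AEs: h_r = −ln(0.58)/24 = 0.545/24 = 0.0227. Median 30.5 weeks, so not reached by week 24. Week-6 risk 12.7%.

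| p_a | −ln(1 − p_a) | Related share of first AEs | Median, any AE (weeks) | Week-6 risk, any AE |
|---|---|---|---|---|
| 60% | 0.916 | 0.545/0.916 = 59% | 18.2 | 20.5% |
| 75% | 1.386 | 0.545/1.386 = 39% | 12.0 | 29.3% |
| 90% | 2.303 | 0.545/2.303 = 24% | 7.2 | 43.8% |
| 95% | 2.996 | 0.545/2.996 = 18% | 5.6 | 52.7% |

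If the related risk were 20%, the share would run from 7.4% to 24.4%; at 10%, from 3.5% to 11.5%. The any-cause curve is a mixture in every case, and the mix depends on a rate that the documents do not supply.

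**3. Why a Kaplan-Meier curve of related AEs is not enough.** Censoring deaths treats the dead as still able to have the event. The cited day-42 mortality is 19% (SECURE) and 33% (VITAL, weighted). With a constant death hazard to week 6, h_d = −ln(0.81)/6 = 0.0351 or −ln(0.67)/6 = 0.0667. Cumulative incidence at week 6 is h_r/(h_r + h_d) × [1 − exp(−6(h_r + h_d))]:
- 19% mortality: 0.0227/0.0578 × (1 − 0.707) = 11.5%
- 33% mortality: 0.0227/0.0894 × (1 − 0.585) = 10.5%

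One minus Kaplan-Meier gives 12.7% in both cases. The overstatement is 1 to 2 percentage points at week 6, and it widens later if deaths continue.

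**The case against.** The strongest reply is that the objective asks for safety to be assessed and does not require a time-to-event analysis. Related AEs and SAEs are summarized at three timepoints, and Protocol 9.9.2.1 also plans description by relationship, severity, seriousness, action and outcome. The study is primarily descriptive, and the SAP does what the protocol says. Relationship may often be Unknown in charts, so an endpoint free of attribution is a defensible companion. All of this stands. It limits the gap to the timing of related events and the precision attached to them, and it is the reason to keep the any-cause curve.

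Three stronger readings are tempting, and the documents do not support them.

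- A reader might infer that the curve describes the underlying illness and not the drug. The any-cause curve includes related AEs, and no rate in the documents shows how far unrelated events dominate. Protocol 9.11 warns that AEs may be incompletely documented, while Protocol section 11 requires explicitly attributed AEs to be recorded, so capture may lean toward related events.
- A reader might divide 42% by an assumed any-AE rate of 80% to 95% and take the 53% to 44% as the related share of first events. That ratio is the share of patients with any AE who ever have a related one.
- A reader might infer that the plan gives any-cause AEs Kaplan-Meier estimates with CIs at weeks 6, 12 and 24. SAP 6.3 specifies those for clinical outcomes; SAP 6.4 promises only summary Kaplan-Meier statistics.

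One limit remains. The shells for Tables 9 to 11 and Figure 5 are in an embedded Excel file that could not be opened, so rows or intervals for related AEs there cannot be ruled out.

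**Conclusion.** The concern holds as a mismatch that should be corrected. The single time-to-event safety analysis targets first AE of any cause, and the objective targets related AEs and SAEs. The related endpoint is tabulated, so the objective is not left unanswered, but on the SAP text it has no CI, no allowance for incomplete follow-up and no timing.

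That conclusion rests on the wording of SAP 2.2, 4.2, 6.1 and 6.4 and needs no numerical assumption. Its size is unknown. The illustrative 18% to 59% related share of first events depends on carrying the SECURE 42% over to 24 weeks of routine practice, on an assumed any-AE risk of 60% to 95%, and on constant, independent hazards. A lower related risk would make the curve less informative about the drug.

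**What to change.** In SAP 6.4:

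1. Make time to first isavuconazole-related AE the main time-to-event safety endpoint, and add time to first isavuconazole-related SAE where numbers allow.
2. Report both as cumulative incidence with death as a competing event, with 95% CIs at weeks 6, 12 and 24.
3. Count an AE as related when the documented relationship is Yes. In a sensitivity analysis, count Unknown as related too.
4. Keep the any-cause first-AE curve as supportive, which also keeps the summary promised in Protocol 9.9.2.1.

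The cost is two extra curves and tables. Relationship and onset date are already on the data collection list, so no new field is needed. Protocol 9.10 says that the EDC keeps durations instead of dates, so the time from index to onset must be available for every AE and not only the first. Intervals for related SAEs will be wide; Protocol 9.11 already concedes that rare safety outcomes may not be estimated reliably. Protocol 9.9 provides for a revised SAP before data collection is complete, and asks for a protocol amendment if the change is judged a major modification of a primary outcome analysis.
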